
To assess gastrointestinal (GI) tolerability across different titration schedules (Cohorts 1 and 2)
	
 • Percentage of subjects with GI AEs at each dose level • Percentage of subjects with nausea and vomiting from baseline (Day 1) over 7 days of treatment

To assess the effect of MEDI0382 on glucose lowering during different meals and times of the day as measured by continuous glucose monitoring (CGM) (Cohort 1 only)
	
 • Change in glucose AUC_{24h} from baseline (Day -1) to the end of dosing at each dose level (Days 7, 14, 21, 28, and 49) • Change in coefficient of variation (ratio of standard deviation: mean) over 24 hours from baseline (Day -1) to the end of dosing at each dose level (Days 7, 14, 21, 28, and 49) • Change in coefficient of variation (ratio of standard deviation: mean) over 7 days at each dose level (Days 1 to 7, Days 8 to 14, Days 15 to 21, and Days 22 to 28) • Change in percentage of time in hyperglycaemia (defined as > 7.8 mmol/l (> 140 mg/dl) and hypoglycaemia (defined as < 3.0 mmol/l (< 54 mg/dl) from baseline (Day-1) over 24 hours to the end of dosing at each dose level (Days 7, 14, 21, 28, and 49) • Change in percentage of time in hyperglycaemia; (defined as > 7.8 mmol/l or (> 140 mg/dl) and hypoglycaemia (defined as < 3.0 mmol/l or < 54 mg/dl) over 7 days at each dose level (Days 1 to 7, Days 8 to 14, Days 15 to 21, and Days 22 to 28) • Change in glucose AUC_{120min} during a standardised meal in the morning from baseline (Day -1) and at the end of 49 days of treatment • Change in glucose AUC_{120min} during a standardised meal in the evening from baseline (Day -1) and at the end of 49 days of treatment

To characterise the effect of MEDI0382 on glucose lowering and weight versus placebo after 7, 14, and 49 days (Cohort 2 only)
	
 • Percentage change in glucose AUC as measured by a standardised MMTT from baseline (Day -1) after 14 and 49 days • Change in fasting plasma glucose from baseline (Day -1) to the end of 7, 14, and 49 days of treatment • Percentage and absolute change in body weight from baseline (Day 1) to the end of 7, 14, and 49 days of treatment • Change in HbA1c from baseline (Day -1 to the end of 49 days of treatment

[REDACTED]
	
[REDACTED]

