Subjects will undergo safety blood tests at any time from Day -7 to Day -3 if the screening visit is more than 7 days before Day 1. On Day -2, subjects will be admitted to the clinical unit for 2 nights and will undergo further initial safety assessments and training in SC injection administration; normal saline will be used for SC injection administration training. At this time an ambulatory blood pressure monitoring (ABPM) device will be fitted on Day -2 and worn for 24 hours; simultaneously a continuous glucose monitoring (CGM) device will be fitted on the contralateral arm and the subject will be given training for CGM use (Figure 3.1.1-1). Subjects will be expected to wear the CGM continuously until the end of dosing. On Day -1, eligibility criteria will be verified and subjects will undergo 2 mixed-meal tolerance test (MMTT) assessments (Meal type A; with serial blood sampling in the morning, and meal type C without serial blood sampling on the evening of that day). Subjects can be randomised after confirming eligibility at any time from Day -1 to Day 1 (predose) to receive either MEDI0382 or placebo. On Day 1, dosing will commence following predose safety measures including vital signs, blood tests for safety, glycated haemoglobin (HbA1c) and exploratory biomarkers, an ECG, and measurement of weight. Since the dose of 50 µg will require a dilution by site staff prior to administration, subjects will have the option to remain as an inpatient or alternatively attend the clinical unit every day for dosing during the first week; during this time subjects will undergo supervision to self-administer the investigational product. On Day 7, safety assessments will be performed and the MMTT meal type B, with serial blood sampling, will be repeated; where relevant, subjects will be discharged home (refer to Section 4.3.1.1 for description of MMTT meal types).

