Note: Whenever vital signs, ECGs, and blood draws are scheduled for the same nominal time, the ECG should occur first, then vital signs, and blood draws should occur last. The timing of the ECGs and/or vital signs should be such that it allows the blood draw (eg, for PK and PD) to occur as close as possible to the scheduled time. Ten minutes of supine rest should precede these assessments.

- a The eligibility check should be based on all clinical measurements and blood tests taken during the screening visit (V1) with the exception of eGFR, liver function tests, blood pressure, urinary illicit drug, alcohol and pregnancy tests, which should be rechecked on Day -2. A targeted physical examination and repeat medical history should also be undertaken to ensure the subject is well enough to commence dosing.
- b The diet of subjects should not be restricted in any way during the study (including during inpatient stay) unless fasting or a standardised meal is specified.
- c Subjects who prefer to attend for daily visits during the first week will be discharged home on Day 1 after all assessments are complete. (X) indicates that subjects can be inpatients or outpatients at these visits.
- d A serum or urine pregnancy test should be conducted on any female subject of childbearing potential as detailed in the schedule. Pregnancy tests do not need to be conducted in women who are surgically sterile (ie, bilateral tubal ligation, bilateral oophorectomy, or complete hysterectomy) or are postmenopausal (defined as at least 1 year since last menses and having an elevated follicle stimulating hormone laboratory value which is in the postmenopausal range in previous laboratory test results).
- e Vital Signs Schedule (blood pressure, heart rate, respiratory rate, and temperature): on days where ABPM is due to be checked a predose set of vital signs should be performed prior to application of the ABPM cuff. Blood pressure should be measured once at heart level in the nondominant arm where possible, opposite to the arm where the CGM device is applied, after the subject has rested in either a seated or supine position for at least 10 minutes. For time points where ECG recording precedes vital sign measurement, the 10-minute rest in the supine position prior to the ECG suffices for the rest prior to vital sign measurement.
 - o Day -2; vital signs to be taken prior to fitting the ABPM device; postural (standing and supine) blood pressures should be performed at this time.

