- m Predose not applicable on Days 7, 29, 36, and 43. An additional blood test for safety (to be taken at any time between Day -3 and Day -7) is not required if the screening visit occurs within 7 days of dosing (Day 1); if the screening visit is more than 7 days prior to dosing on Day 1, then additional safety blood tests should be taken (as described in Section 4.3.3).
- n PK Sampling Schedule for MED10382:
Day -1; No specific time point
Day 1; Predose
Day 7 and Day 15; Predose
Day 22; Predose, 1, 2 (± 15 min); 4, 6, 8, and 12 (± 30 min) hours postdose
Day 23: Predose
Day 29; 36; 43 Predose
Day 49; Predose, 1, 2 (± 15 min); 4, 6, 8, and 12 (± 30 min) hours postdose
Day 50; Predose

^o ADA Sampling Schedule: Day 1 predose; Day 29 predose; Day 50 predose; and 28 days after administration of the last dose in the study

■ [REDACTED]

^q Capillary blood ketone (point-of-care testing) and serum beta-hydroxybutyrate will be measured at baseline after at least 10 hours fasting on Day -1 and predose and 4 hours postdose on Day 22, and Day 49 with fasting for at least 10 hours the night before.

^r MMTT Type A and B Schedule: Following a minimum 10-hour fast overnight and 2.5 hours after taking the IP, a blood sample for glucose (Type B) or glucose metabolism panel [REDACTED] will be taken immediately prior (within 15 minutes) to the subject drinking one entire can of Ensure Plus as a standardised meal (ie, “0 minutes”). Blood samples for glucose metabolism panel will additionally be drawn at 15, 30, 45, 60, 90, 120, 180, and 240 minutes (\pm 5 min) after consumption of the standardised meal.

^s MMTT Type C Schedule: the subject should be fasted from 1400 hours (\pm 15 min) and receive water only from this time until 2000 hours. A standardised liquid meal (one entire can of Ensure Plus) should be administered to the subject at 1800 hours. The subject should ensure that they are wearing their CGM device before, during, and after the test. No additional blood tests are required to be taken during this period, and the subject will be permitted to eat and drink freely from 2000 hours onwards.

^t CGM device should be worn continuously throughout the study and the sensor should be applied to the arm, taking into account subject preference and which side the ABPM device will be used on. The sensor applied to the skin is single-use and may not be re-attached once removed.

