4.3 Description of Study Procedures

4.3.1 Efficacy

4.3.1.1 Mixed-meal Tolerance Tests

Following a minimum 10-hour fast the subject will undergo an MMTT which will involve the consumption of a standardised liquid meal (Ensure Plus, a nutritional supplement containing the components of fat, carbohydrate, and protein, which make up a standard MMTT) within 5 minutes, and timed serial blood samples will be obtained for measurement of glucose and parameters related to glucose metabolism through 240 minutes after

consumption of the standardised meal (with no additional food intake during this time). The MMTT procedures will be performed at the time points specified in the schedules of procedures by cohort.

For Cohort 1 blood will be drawn within 15 minutes before consuming the standardised liquid meal (ie, “0 minutes”), and at 15, 30, 45, 60, 90, 120, 180, and 240 minutes (± 5 minutes) after consumption. Blood sampling should occur as close as possible to the specified times for the MMTT. Sampling ± 5 minutes of the specified time will not be considered a protocol deviation but the exact time of sampling should be recorded.

For Cohort 2, blood will be drawn within 15 minutes before consuming the standardised liquid meal (ie, “0 minutes”), and at 5, 10, 15, 30, 45, 60, 90, 120, 180, and 240 minutes (± 5 minutes) after consumption.

For clarity, MMTTs have been subdivided into Types A, B, and C; according to the timing of the test, and differences in blood sampling schedules.

Ingestion of standardised liquid meals/Ensure as part of an MMTT Type A or B, where relevant, should occur after blood sampling for PK, 2.5 hours after investigational product administration and PD sampling should be arranged in accordance with this schedule.

Mixed-meal Tolerance Test Type A (Cohorts 1 and 2)

[REDACTED]
[REDACTED]
[REDACTED]
[REDACTED] Glucose measurements from these pre- and post-MMTT samples will be used for the primary efficacy assessment and secondary endpoints including fasting glucose and AUC glucose 7 days at the 50 μ g dose level. All MMTT test results will be used to generate PD profiles.

Mixed-meal Tolerance Test Type B (Cohorts 1 and 2)

All timings and procedures are identical to MMTT Type A except for PD sampling which should be for collection of blood glucose samples only.

Mixed-meal Tolerance Test Type C – Cohort 1 only

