3.5 Exploratory Pharmacodynamic Endpoint(s) and Analyses

3.5.1.1 Pharmacodynamic Endpoint(s)

- [REDACTED]
- Change in CGM glucose AUC_{0-24h} from baseline (Day -1) to the end of each dosing level for titration and treatment (Cohort 1 only)
- Change in coefficient of variation (CV) (ratio of standard deviation: mean) of CGM glucose values over 24 hours from baseline (Day -1) to the end of each dosing level for titration and treatment (Cohort 1 only)
- CV of CGM glucose values over 7 days at each dose level (Days 1 to 7, Days 8 to 14, Days 15 to 21, and Days 22 to 28) (Cohort 1 only)
- Change in percentage of time in hyperglycemia (defined as > 7.8 mmol/l or > 140 mg/dl as measured by CGM) over 24 hours from baseline (Day -1) to the end of each dosing level for titration and treatment periods (Cohort 1 only)
- Change in percentage of time in hypoglycemia (defined as < 3 mmol/l or < 54 mg/dl as measured by CGM) over 24 hours from baseline (Day -1) to the end of each dosing level for titration and treatment periods (Cohort 1 only)

- Percentage of time in hyperglycemia (defined as > 7.8 mmol/l or > 140 mg/dl as measured by CGM) over 7 days at each dose level (Days 1 to 7, Days 8 to 14, Days 15 to 21, and Days 22 to 28) (Cohort 1 only)
- Percentage of time in hypoglycemia (defined as < 3 mmol/l or < 54 mg/dl as measured by CGM) over 7 days at each dose level (Days 1 to 7, Days 8 to 14, Days 15 to 21, and Days 22 to 28) (Cohort 1 only)
- CGM glucose AUC_{0-4hr} during MMTT (type A) on baseline (Day -1) and Day 49 and during MMTT (type B) on Day 7 (Cohort 1 only)
- CGM glucose AUC_{0-2hr} during morning MMTT (type A) on baseline (Day -1) and Day 49 (Cohort 1 only)
- CGM glucose AUC_{0-2hr} during evening MMTT (type C) on baseline (Day -1) and Day 49 (Cohort 1 only)
- The change in insulin AUC_{0-4hr}, glucagon AUC_{0-4hr}, and active and total (the sum of active and inactive GLP-1) GLP-1 AUC_{0-4hr} from baseline (Day -1) to Day 49 (Cohort 1 and 2)
- The change in pre-meal (i.e., time 0 basal/fasting) values of insulin, glucagon, and active and total (the sum of active and inactive GLP-1) GLP-1 from baseline (Day -1) to Day 49 (Cohort 1 and 2)
For Cohort 1 only, the fasting plasma insulin value on Day 7 will also be summarized
- The change in fasting C-peptide from baseline (Day -1) to Day 7 and Day 49 (Cohort 1 only)
- The change in serum beta-hydroxybutyrate concentration from baseline (Day -1) to Days 22 and 49 (pre-dose and 4 hr post-dose) (Cohort 1 only)

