3.5.1.2 Analysis of Pharmacodynamic Endpoint(s)

All of the PD measures will be summarized by scheduled visits. Except for the analyses specified in the following of this section, all of the other PD endpoints will be analyzed for the end-of-treatment measure only using similar ANCOVA model as that in the primary analysis. Treatment effect and baseline value (if available) will be added in the model.

[REDACTED]

[REDACTED]

The CV of CGM glucose values over 7 days at each dose level will be analyzed with a 2-sample t-test (assuming equal variance).

The change in percentage of time in hyperglycemia and hypoglycemia over 24 hours from baseline (Day -1) to Day 49 will be analyzed with the Wilcoxon rank sum test.

The percentage of time in hyperglycemia and hypoglycemia over 7 days at each dose level will be analyzed with the Wilcoxon rank sum test.

The morning (type A) and evening (type C) MMTT CGM glucose AUC_{0-2hr} on baseline (Day -1) and Day 49, will be summarized. Their difference and agreement will be analyzed by the paired t-test and the concordance correlation coefficient, respectively. The CGM glucose AUC_{0-4hr} during MMTT on baseline (Day -1), Day 7, and Day 49, and the corresponding plasma glucose AUC_{0-4hr} will be summarized and analyzed in a similar manner.

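### The 24-hour CGM changes compare at-home days with a meal-test baseline day, and the SAP plans an estimated difference from placebo only at end of treatment

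*SAP*

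**What the plan says.** SAP 3.5.1.1 defines the change in CGM AUC0-24h and in 24-hour coefficient of variation (CV) "from baseline (Day -1) to the end of each dosing level for titration and treatment (Cohort 1 only". The 24-hour percentages of time in hyper- and hypoglycaemia are defined in the same way. The SAP gives no day numbers. The protocol synopsis does, taking the change "to the end of dosing at each dose level (Days 7, 14, 21, 28, and 49".

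SAP 3.5.1.2 summarises all PD measures. Apart from listed exceptions, it says "all of the other PD endpoints will be analyzed for the end-of-treatment measure only", using the ANCOVA of the primary analysis. The 24-hour percentages of time are an exception, but their rank sum test is also limited to the change from Day -1 to Day 49.

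On the baseline day, according to protocol 3.1.1, "subjects will undergo 2 mixed-meal tolerance test (MMTT) assessments (Meal type A; with serial blood sampling in the morning", followed by a Type C test that evening. In the morning test (Table 4.2.2-1, footnote r) a blood sample is taken just before the "subject drinking one entire can of Ensure Plus as a standardised meal". Section 4.3.1.1 adds 240 minutes "with no additional food intake during this time". For the evening test (footnote s) subjects fast from 1400 "and receive water only from this time until 2000 hours", apart from one can at 1800.

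For other days, footnote b states: "The diet of subjects should not be restricted in any way during the study (including during inpatient stay", with an exception only where fasting or a standardised meal is specified.

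**The concern.** The exploratory CGM objective is glucose lowering at different meals and times of day, and the 24-hour endpoints are defined at each dose level. A change from baseline can be read as a drug effect within an arm only if the baseline day and the later day are otherwise alike. Here food intake is fixed by the protocol for much of Day -1 and is free on the days that represent 100 µg, 200 µg and early 300 µg.

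The placebo arm goes through the same move from test day to ordinary day, so the difference between arms is the natural way to remove it. The SAP plans to estimate that difference only at the end of treatment, which is the one day whose meal pattern matches baseline. A reader of the dose-level tables could take the within-arm profile from Day 7 to Day 49 as a dose-response or time-course when part of it is diet. The step from Day 28 to Day 49 is the clearest case: the dose is 300 µg on both days, but one is an ordinary day and the other a test day.

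**Working it through.** The plan states no figure on this point, so there is none to reproduce. The check sets each CGM day beside its meal conditions and its planned analysis.

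**Inputs.** Days: protocol synopsis. Dose levels: protocol 3.1.2. Meal tests, visit days and fasts: protocol 3.1.1, 4.3.1.1 and Table 4.2.2-1 with footnotes b, j, l, r and s. Analyses: SAP 3.1 and 3.5.1.2.

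| Day | Dose | Setting | Standardised cans | Match to Day -1 | SAP analysis of 24-hour change |
|---|---|---|---|---|---|
| -1 | none | inpatient | 2 | baseline | – |
| 7 | 50 µg | clinic | 1 (morning) | partial | summary by arm |
| 14 | 100 µg | at home | 0 | no | summary by arm |
| 21 | 200 µg | at home | 0 | no | summary by arm |
| 28 | 300 µg | at home | 0 | no | summary by arm, if produced |
| 49 | 300 µg | inpatient | 2 | yes | ANCOVA or rank sum test |

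Clinic days after Day 7 are 15, 22–23, 29, 36, 43 and 49–50, so Days 14, 21 and 28 are not visits. The only required fast touching them is the overnight fast starting on the night of Day 21. Three of the five post-baseline days are therefore unmatched, one is partly matched and one is matched.

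**Other CGM measures.** SAP 3.5.1.2 compares 7-day CV (two-sample t-test) and 7-day percentage of time in hyper- and hypoglycaemia (rank sum test) between arms for Days 1–7, 8–14, 15–21 and 22–28. These use on-treatment values without the Day -1 baseline, so the mismatch does not enter. AUC0-24h has no 7-day counterpart.

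**Protocol against SAP.** Protocol 4.8.3.3 plans ANCOVA for exploratory continuous endpoints with no end-of-treatment limit. It refers to Section 2.3, where the available copy of the table shows the percentage-of-time endpoints with these days; AUC24h and 24-hour CV appear in the synopsis.

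**How the shift enters.** Let d be the drug effect and s a diet shift common to both arms. Then:

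- within-arm change on MEDI0382 = d + s
- change on placebo = s
- difference = (d + s) − s = d

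Illustration with assumed values, d = −1 SD and s from −0.5 to +1 SD:

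| s (SD) | Within-arm change (SD) | Difference from placebo (SD) |
|---|---|---|
| −0.5 | −1.5 | −1.0 |
| 0 | −1.0 | −1.0 |
| +0.5 | −0.5 | −1.0 |
| +1.0 | 0.0 | −1.0 |

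**Precision of the missing estimate.** With 26 and 13 subjects, half-width = t(37) × √(1/26 + 1/13) SD, and √(1/26 + 1/13) = √(3/26) = 0.340. The 95% half-width is 2.026 × 0.340 = 0.69 SD. A 90% interval, which would go with the general 0.1 level in SAP 3.1, gives about 0.57 SD. Both are before any gain from the baseline covariate.

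**The case against.** A reader might infer that there is no placebo comparison at all on the earlier days. The documents do not support that. SAP 3.1 presents tables by cohort and treatment group, so placebo sits beside MEDI0382 and a common shift can be seen. The 7-day CV and percentage of time are tested between arms at every dose level. What is missing is an estimated difference with an interval for the 24-hour changes, and for AUC0-24h nothing else fills that gap.

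A reader might also infer that subjects take two cans and nothing else until 2000 on Day -1. That is not established. The timing of 2.5 hours after dosing cannot apply to Day -1, because dosing starts on Day 1, and no clock time is set for that morning test. If the can were taken at 0800 (an assumption), the 4-hour test would end at 1200 and leave two hours of free eating before 1400. Subjects also eat freely from 2000. The day is still unlike Days 14, 21 and 28.

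Day 28 comes from the protocol's list. The SAP wording, read literally, gives Day 49 as the end of the 300 µg level, so a 24-hour Day 28 value may not be produced. This objection stands as to the SAP, and is a reason for it to name its days.

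Finally, restricting formal analysis to end of treatment is a consistent SAP choice (3.4.3 does the same for Cohort 2), it tests the diet-matched day, and the endpoints are exploratory. Estimating four endpoints on four more days adds 4 × 4 = 16 comparisons with only 13 placebo subjects and no multiplicity adjustment. That argues for presenting them as estimates; it does not make the within-arm changes interpretable.

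**Conclusion.** The point holds as an interpretation problem in exploratory endpoints. Within-arm 24-hour change on Days 14, 21 and 28 is drug effect plus the move from a meal-test day to an ordinary day. Day 7 is affected in part, and any Day 28 to Day 49 pattern is open to the same reading. The SAP's end-of-treatment limit leaves these days without an estimated difference from placebo.

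Neither the size nor the direction of the diet shift can be taken from the documents. The illustration in SD units shows only the mechanism. The conclusion that the difference between arms removes the shift assumes that the shift is common to both arms, which randomisation and the shared schedule make reasonable. Reduced intake caused by the drug would remain in the difference, where it belongs as part of the drug effect. Day -1 can stay as the ANCOVA covariate: it is measured before dosing in both arms, so a diet mismatch limits its gain in precision without biasing the comparison.

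The Day 49 comparison keeps its diet match, and the primary and secondary results are untouched. This is a cheap improvement and not a flaw in the trial's main conclusions.

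**What to change.** In SAP 3.5.1.1, name the days for the 24-hour CGM endpoints as in the protocol: 7, 14, 21, 28 and 49. This also settles whether values are produced for Days 14, 21 and 28, since 3.5.1.2 summarises PD measures by scheduled visit and these are not visit days.

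In SAP 3.5.1.2, report MEDI0382 minus placebo with its confidence interval at Days 7, 14, 21 and 28 as well as Day 49. Use the stated ANCOVA for AUC0-24h and 24-hour CV, and the stated rank sum test with an estimated shift (for example Hodges-Lehmann) for the percentages of time.

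Footnote the tables to say that within-arm changes at Days 7 to 28 cannot be read as drug effect alone, because intake on those days differs from Day -1.

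The cost is four more analyses per endpoint and a few lines of SAP text, on CGM data already planned for collection. The downside is more exploratory comparisons with wide intervals, so they should be presented as estimates and not as tests of each dose level.
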